1.2 Study objectives and endpoints

[figure not shown]
Table 1-1 Objectives and related endpoints

[figure not shown]
Objective(s)	Endpoint(s)
Primary objective(s)	Endpoint(s) for primary objective(s)

 To evaluate the efficacy of retreatment with ligelizumab 72 mg or 120 mg q4w in subjects previously treated in the core studies (CQGE031C2302/CQGE031C2303) To evaluate the efficacy of retreatment with ligelizumab in the subgroup of these subjects who achieved a weekly urticaria activity score (UAS7) ≤ 6 after 12 weeks of treatment in these core studies 	
 The proportion of subjects with well-controlled disease (UAS7 ≤ 6) at Week 12
Secondary objective(s)	Endpoint(s) for secondary objective(s)
For retreatment efficacy evaluation:	

 To describe the efficacy of ligelizumab 72 mg or 120 mg q4w in achieving complete control of chronic spontaneous urticaria (CSU) at Week 12 when used as retreatment for subjects previously treated in the core studies (CQGE031C2302/CQGE031C2303) To describe the efficacy of ligelizumab with respect to a reduction from extension study baseline in the UAS7 and its components (weekly itch severity score (ISS7) and weekly hives severity score (HSS7) at Week 12 in all subjects receiving the same dose regimen as in the core studies, i.e. 72 mg or 120 mg q4w To describe the efficacy of ligelizumab in achieving an angioedema-free period at Week 12 in all subjects receiving the same dose regimen as in the core studies, i.e. 72 mg or 120 mg q4w 	
 The proportion of subjects with completely controlled disease (UAS7 = 0) at Week 12 Absolute change from extension study baseline in the UAS7 and its components (ISS7 and HSS7) at Week 12 Cumulative number of weeks that subjects achieve weekly angioedema activity score (AAS7) = 0 between extension study baseline and Week 12

Objective(s)	Endpoint(s)

To describe the efficacy of ligelizumab in achieving Dermatology Life Quality Index (DLQI) = 0-1 at Week 12 when used as re-treatment for all subjects receiving the same dose regimen as in the core studies, i.e. 72 mg or 120 mg q4w	
Percentage of subjects achieving DLQI = 0-1 at Week 12
For self-administration efficacy evaluation:	

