2.5.2 Statistical hypothesis, model, and method of analysis

No inferential statistical methods are planned. Descriptive statistics will be used to summarize data.

Retreatment efficacy of ligelizumab 120 mg q4w or 72 mg q4w in achieving well-controlled CSU at Week 12 in the first half of the treatment period will be evaluated in subjects transitioning from the core studies. The primary analysis will be performed for subjects receiving the same dose of ligelizumab they received in the core studies, i.e. 72 mg or 120 mg for one year.

For subjects rolling over from study CQGE031C2302 and CQGE031C2303 (i.e. two core studies) and treated with same ligelizumab dose regimen, summary statistics for the proportion of subjects achieving $UAS7 \leq 6$ response will be provided by treatment group in core studies, and by visit starting from Visit 201 up to Visit 204 (i.e. Week 12 of the first half of the treatment period). The corresponding 95% confidence interval for response rate also will be derived based on the score method including continuity correction (Newcombe, 1998).

For the subgroup of subjects who achieved $UAS7 \leq 6$ at Week 12 in the core studies, and who received either 72 mg or 120 mg ligelizumab, the proportion of subjects with the response of $UAS7 \leq 6$ at Week 12 of the first half of the treatment period in this extension study will be provided together with a 95% confidence interval.

Subjects rolling over from study CQGE031C2302 and CQGE031C2303, who received different treatment or different ligelizumab dose regimen, will not be included in the primary analysis for re-treatment efficacy.

Subjects rolling over from study CQGE031C1301, who received ligelizumab 120 mg, will not be included in this primary analysis.

Subjects rolling over from the adolescent PK/PD study CQGE031C2202 will also not be included in this primary analysis, as they received treatment doses of ligelizumab of 24 mg or 120 mg for different treatment times.

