2.5.3 Handling of missing values/censoring/discontinuations

The UAS7 score is derived from the sum of the HSS7 score and the ISS7 score, as noted above. The HSS7 and ISS7 score will be derived by adding up the daily HSS and ISS scores of the 7 days preceding the visit, respectively. The daily score (HSS and ISS) will be calculated by averaging the morning and evening HSS and ISS score, respectively. If one of the morning or evening scores is missing, the non-missing score for that day (morning or evening) will then be used as the daily score.

A minimum of 4 out of 7 daily scores are needed to reliably calculate a weekly HSS7, ISS7 or UAS7 score. For each weekly score from UPDD (i.e. HSS7, ISS7 and UAS7 score), if one or more of the daily scores are missing, the following principles will be applied to handle the missing data:

- If a subject has at least 4 “non-missing” daily scores within the 7 days prior to the study visit, the weekly score will be calculated as the sum of the available eDiary scores of that week, divided by the number of non-missing days, multiplied by 7.
- If there are less than 4 “non-missing” daily scores within the prior 7 days, then the weekly score will be considered as missing for that week.

Subjects who discontinue from study treatment early will be encouraged to stay in the study following the procedures described in the study protocol Section 9.1.1. These are considered as retrieved dropout (RDO) subjects.

The primary analysis will account for different post-dosing events for missing data handling as follows:

- Discontinuation of initially assigned study treatment prior to Week 12 (Visit 204) due to AEs or lack of efficacy or any other reasons, except for the reason of study early termination: Retrieved dropout (RDO) data collected after study treatment discontinuation will be used for analysis. If no RDO data was collected after study treatment permanent discontinuation, non-responder imputation will be applied for missing data imputation.
- Discontinuation of initially assigned study treatment prior to Week 12 (Visit 204) due to study early termination: the efficacy data collected after the discontinued treatment will be censored. The missing data caused by this intercurrent event occurrence will be imputed based on the treatment arm (ligelizumab 72 mg or 120 mg q4w) data under the missing at random (MAR) assumption using multiple imputation separately.

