- Use of protocol allowed rescue medication prior to Week 12 of the first half of the treatment period (V204): Efficacy data collected during intake of rescue medication will not be excluded from the analysis. H1-AH is being used as rescue medication in addition to background medication. Considering that, the patient population are refractory to H1-

AHs and that ligelizumab efficacy is being evaluated on top of H1-AH therapy, all data collected will be used for analysis.

For missing or censored UAS7/HSS7/ISS7 scores due to all other reasons, non-responder imputation will be applied for missing data imputation.

Multiple imputation (MI)

Multiple imputation is a simulation based approach where missing values are replaced by multiple Bayesian draws from the conditional distribution of missing data given the observed data and covariates, creating multiple completed data sets. These completed data sets can then be analyzed using standard methods. Rubin (1987) presented rules how to combine the multiple sets of estimates to produce overall estimates and confidence intervals that adequately incorporate missing data uncertainty. The multiple imputation analysis will be imputed based on the individual treatment arm information.

Missing values for the “change from baseline UAS7 score” will be imputed separately for each treatment group including region, CU index and baseline UAS7 score in the model.

Specifically, the missing data will be imputed following the steps below:

1. Impute the following missing data which will be used for primary analysis following the MAR assumption.
 - The intermittent missing data;
 - Missing data with intercurrent events handled through hypothetical strategy.

The missing data not fit in to the categories above will not be imputed in this step.

The imputed results will be transferred back for the imputed values on the primary endpoint “proportion of $UAS7 \leq 6$ at week 12.”

2. Impute the rest missing data of the primary efficacy endpoint with non-responder imputation.

Duplicate data handling of questionnaires

For HSS7, ISS7, the daily score is derived from the average of morning and evening scores. All other questionnaires are completed either daily or at visits. If any of those questionnaires are completed more than once per day or visit (depending on the questionnaire schedule), then the worst outcome (i.e. the highest score) of the duplicate observations will be used in the analysis.

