3.1 Primary endpoint(s)

The total number of subjects enrolled will be determined by the drop-out rate prior to the Phase 3 extension study from studies CQGE031C2302, CQGE031C2303, CQGE031C2202 and CQGE031C1301.

Based on interim results from CQGE031C2201, it is assumed that the proportion of subjects achieving $UAS7 \leq 6$ at Week 12 is around 55% for ligelizumab 72 mg q4w. It is assumed that the well-controlled response for ligelizumab 120 mg q4w will be similar. The corresponding 95% confidence interval is listed based on different assumptions of number of subjects who will be enrolled for each treatment arm.

Table 3-1 95% confidence interval based on number of subjects enrolled from the core studies (CQGE031C2302/2303)

Number of subjects enrolled	Number of subjects for each treatment group	Drop out rate at Week 12	Assumed proportion of subjects achieving $UAS7 \leq 6$ at Week 12	Corresponding 95% confidence interval
500	250	10%	55%	(48.6% - 61.6%)
900	450	10%	55%	(50.2% - 59.9%)
1200	600	10%	55%	(50.8% - 59.2%)

To evaluate the retreatment efficacy in the subgroup of subjects who achieved $UAS7 \leq 6$ at Week 12 after the retreatment on the same ligelizumab dose, the 95% confidence interval of the

response rate will be provided for each treatment group. It is assumed that 50% of subjects enrolled into this extension study were well-controlled responders during the core studies for each ligelizumab treatment group. A 15% drop out rate is assumed for each treatment group before Week 12. The number of subjects required at the baseline of re-treatment for each treatment arm is listed in Table 3-2 below, based on different assumptions of the retreatment response rates and the corresponding precision levels (width of the 95% confidence interval).

Table 3-2 Number of subjects required at the baseline of re-treatment for each treatment arm enrolled from the core studies (CQGE031C2302/2303)

Response rate after retreatment	Precision		
	10%	12%	15%
70%	191	135	85
80%	146	102	66
90%	83	59	38

4 Change to protocol specified analyses

Not applicable.

5 Appendix

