5.5 Statistical models and SAS sample code

5.5.1 Primary analysis

The primary analysis will be performed based on the data after the missing data imputation for the intercurrent events has been performed.

Step 1:

The SAS procedure `proc mi` will be used for multiple imputation for change from baseline in UAS7 score with the following sample code:

```
proc mi data=... out=... nimpute=... seed=123;  
by group;  
class ige cuind group;  
fcs reg(/details);  
var ige cuind group baseline wk12cfb;  
run;
```

where `group` = treatment group
`ige` = baseline IgE
`cuind` = baseline CU index
`baseline` = baseline UAS7 score
`wk12cfb` = change from baseline UAS7 score at Week 12 in TRT1.

If the imputation model does not converge, remove the covariates as needed until it converges.

The following SAS sample code will be used to transfer the continuous variable change from baseline in UAS7 score to a binary response of $UAS7 \leq 6$, and conduct non-responder imputation for subjects who discontinued due to study early termination:

```
data ...;  
set ...;  
resp = (baseline + wk12cfb) <= 6;  
if flag = 0 then resp = 0;  
run;
```

where `resp` = binary response of $UAS7 \leq 6$
`baseline` = baseline UAS7 score
`wk12cfb` = change from baseline UAS7 score at Week 12 in TRT1
`flag` = flag of missingness
(1 = missing due to study early termination, 0 = missing not due to study early termination, . = data is observed).

Note that the order of multiple imputation and non-responder imputation could be reversed as needed.

Step 2:

The SAS procedure `proc freq` will be performed to calculate the primary endpoint (binary response of $UAS7 \leq 6$ at Week 12) for each imputed dataset with the following sample code:

```
proc freq data = ...;  
by _imputation_group;  
tables resp /nopercnt nocol norow nocum binomial(level = "1" cl =  
wilson(correct));  
output out = sumstat binomial;  
run;
```

where `_imputation_` = the index for imputation times

group = treatment group

resp = binary response of UAS7≤6

sumstat is the dataset which includes the response rate estimate and the standard error in each group

Here “cl = wilson(correct)” is used to calculate the 95% confidence intervals by Wilson score method with continuity correction.

Step 3:

Rubin’s Rule:

Rubin’s Rule will be applied to combine the multiple sets of estimates to produce the overall estimates, standard error, confidence interval and p-values.

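### The primary imputation model omits core-study Week 12 response; if run on whole treatment arms, it may understate the retreatment rate in core responders

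*SAP*

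**What the plan says.** **Populations.** The primary objective in SAP 1.2 (Table 1-1) has two parts. The second reads "To evaluate the efficacy of retreatment with ligelizumab in the subgroup of these subjects who achieved a weekly urticaria activity score" of 6 or less at core-study Week 12. SAP 2.5.2 gives this group its own estimate and 95% interval: "and who received either 72 mg or 120 mg ligelizumab, the proportion of subjects with the response of" UAS7 ≤ 6 is reported at extension Week 12. SAP 2.2.2 and 2.14.1 define it as the responder retreatment subpopulation, and Table 2-16 lists it for the UAS7 ≤ 6 endpoint.

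**What is imputed.** For treatment stopped by study termination before Week 12, SAP 2.5.3 says that missing values "will be imputed based on the treatment arm (ligelizumab 72 mg or 120 mg q4w) data under the missing at random (MAR) assumption". Step 1 of its procedure covers intermittent missing data and "Missing data with intercurrent events handled through hypothetical strategy". Remaining missing values become non-response.

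**The model.** In the text of SAP 2.5.3, missing changes in UAS7 "will be imputed separately for each treatment group including region, CU index and baseline UAS7 score in the model". The code in SAP 5.5.1 runs by treatment group with "var ige cuind group baseline wk12cfb", which has IgE where the text has region. Neither list contains core-study Week 12 UAS7 or response.

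**The input.** The call is "proc mi data=... out=... nimpute=... seed=123". The dataset name is left blank.

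**Planning values.** SAP 3.1 assumes about 55% response at Week 12 overall. For the subgroup it says: "It is assumed that 50% of subjects enrolled into this extension study were well-controlled responders during the core studies for each ligelizumab treatment group". Table 3-2 then takes 70, 80 or 90% as alternative retreatment rates in those responders.

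**The concern.** When imputed data are later split by a variable, the imputation model should contain that variable. Otherwise the draws treat it as uninformative given the other covariates, and any real difference between the groups is diluted among the imputed subjects. Here the split is by core response, and the result it produces is a primary one.

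The listed covariates may not stand in for core response. Treated subjects must have relapsed to UAS7 ≥ 16 (protocol 3.1 and 5.1), so extension baseline UAS7 is restricted in range and reflects the severity of the relapse. SAP 5.5.1 also allows covariates to be dropped until the model converges. At stake is a downward shift in the responder-subgroup rate that its confidence interval would not reveal.

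**Working it through.** **1. The plan's own figure.** Table 3-2 is reproduced by n₀ = 1.96² p(1 − p)/h², rounded up, then N = n₀/(0.85 × 0.50), rounded up. At h = 10 points:

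- p = 0.70: 80.7 → 81; 81/0.425 = 190.6 → 191
- p = 0.80: 61.5 → 62; 62/0.425 = 145.9 → 146
- p = 0.90: 34.6 → 35; 35/0.425 = 82.4 → 83

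All nine cells match with h as the half-width of the interval. Read as a full width, the 10% column would need 760, 579 and 328. The planned precision is therefore ±10 to ±15 points.

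**2. What the planning values imply if combined.** The SAP does not combine them; this is an illustration. With 55% overall and half the subjects core responders at rate r, the core non-responder rate is (55 − 0.5r)/0.5 = 110 − r. That is 40, 30 or 20% for r = 70, 80 or 90%.

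**3. Shortfall.** Let f be the share of core responders whose Week 12 value is multiply imputed. Suppose that imputation uses the whole arm and that the listed covariates carry no information on core response. Imputed responders are then drawn at about 55% instead of r, and the shortfall is f × (r − 55):

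| f | r = 70% | r = 80% | r = 90% |
|---|---|---|---|
| 0% | 0 | 0 | 0 |
| 5% | 0.75 | 1.25 | 1.75 |
| 10% | 1.5 | 2.5 | 3.5 |

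In subjects: Table 3-1's largest scenario has 600 per arm, so 300 core responders. At f = 10%, 30 are imputed. At r = 80%, 24 should respond, but the model draws about 0.55 × 30 = 16.5. The gap is 7.5/300 = 2.5 points.

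**4. Overall population.** If f is the same in core responders and non-responders, the errors cancel: 0.5f(55 − r) + 0.5f(55 − (110 − r)) = 0.

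**5. Simulation.** Regression imputation within an arm of 250 was run with and without a core-response flag (400 runs, 20 imputations). Baseline mean 29, SD 7, residual SD 11 and correlation 0.3 are assumptions, not values from the documents. At f = 15%, the responder rate without the flag was lower than with it by 2.2, 3.4 and 4.8 points for r = 70, 80 and 90%. The formula gives 2.25, 3.75 and 5.25. The overall rate was essentially the same under both models. If core response did not predict (55% in both groups), the two models agreed to within about 0.1 point. Both models also fell somewhat below the true rate; this reflects normal imputation under the assumed score distribution and is a separate matter.

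**The case against.** **The bias is not established as fact.** A reader might infer that the responder rate will be understated. The PROC MI input is blank, the endpoint is listed for three populations in Table 2-16, and the interval formula in SAP 5.5.1 uses the subgroup sample size. If imputation were run on the responder subpopulation alone, donors would be responders and the effect would vanish. A sentence in SAP 5.5.1 also assigns non-response to subjects who discontinued because of termination. The flag code there, and SAP 2.5.1.1 and 2.5.3, contradict it, but if followed it would remove this mechanism. This objection stands: the effect is conditional. The treatment-arm wording in SAP 2.5.3 favours whole-arm imputation without settling it.

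**The size is unknown.** The 55% comes from interim results of an earlier study, and the 70 to 90% are inputs to a precision table, so the SAP does not plan a contrast between them. Nor can the 15% dropout in SAP 3.1 stand for f, because ordinary dropout without retrieved data is set to non-response. Both points stand.

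**The consequences are limited.** The analysis is descriptive, with no test. One might infer an inflated core non-responder rate, but none is reported. One might also want core response in the UAS7 = 0 and change-from-baseline models, but Tables 2-9 and 2-16 do not analyse those endpoints by core response.

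**The added covariate is not free everywhere.** The FAS includes subjects from C2202 and C1301, who have no core-study Week 12 score, and subjects whose core score reflects omalizumab or placebo. This stands and limits where the change applies.

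**Conclusion.** The omission is certain: neither the text nor the code conditions on the variable that defines the second primary population. The resulting bias is conditional on three things: imputation at arm level, core response predicting retreatment response given the other covariates, and a non-trivial number of core responders being imputed. The planning values suggest the second condition but do not prove it.

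Under all three, the understatement is about f × (r − 55) points, and smaller if the covariates carry part of the information. At r = 80% and f = 10%, the shortfall is a quarter of the tightest planned half-width (2.5 of 10 points); at f = 5% it is an eighth. No bias in the overall retreatment estimate follows, provided termination missingness is unrelated to core response. The point merits a correction because the remedy is small and the estimate is primary.

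**What to change.** For the primary UAS7 ≤ 6 analysis, the SAP should:

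- State which dataset enters PROC MI and whether imputation is run once or separately for each population.
- Run it in the same-dose retreatment subpopulation, by treatment arm.
- Add core-study Week 12 UAS7 or the core response flag as a covariate, or impute within arm by core-response status. Keep this variable if others are dropped for convergence.
- Report how many subjects, and how many core responders, have a multiply imputed Week 12 value in each arm, so that f is visible.

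The UAS7 = 0 and change-from-baseline models need no change on this ground. The FAS analysis of UAS7 ≤ 6 needs its own imputation run without the core variable. The cost is one covariate that is already needed to define the subgroup, a separate imputation run for the FAS, and possibly some strain on convergence.

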12.4.2 Statistical model, hypothesis, and method of analysis

To show retreatment efficacy of ligelizumab 120 mg q4w or 72 mg q4w in achieving well-controlled CSU at Week 12 in the first half of the treatment period in subjects transitioning from the core studies, the summary statistics for the proportion of subjects achieving $UAS7 \leq 6$ at Week 12 of the first half of the treatment period in this extension study will be provided. The primary analysis will be performed for subjects receiving the same dose of ligelizumab they received in the core studies, i.e. 72 mg or 120 mg for one year. The corresponding 95% confidence interval also will be derived based on the score method including continuity correction.

For the subgroup of subjects who achieved $UAS7 \leq 6$ at Week 12 in the core studies, and who received either 72 mg or 120 mg ligelizumab, the proportion of subjects with the response of $UAS7 \leq 6$ at Week 12 of the first half of the treatment period in this extension study will be provided together with a 95% confidence interval.

Subjects rolling over from study CQGE031C1301, who received ligelizumab 120 mg, will not be included in this primary analysis. As this is an open-label Japan safety study, the efficacy data for these subjects will be analyzed separately to avoid potential confounding issues.

Subjects rolling over from the adolescent PK/PD study CQGE031C2202 will also not be included in this primary analysis, as they received treatment doses of ligelizumab of 24 mg or 120 mg for different treatment times. The efficacy data for these subjects will be analyzed separately.

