The SAS procedure proc mianalyze will be used for this analysis with the following code:

```
ods output ParameterEstimates = pe_comb VarianceInfo = var_comb;
proc mianalyze data = sumstat;
by group;
ModelEffects _BIN_;
stderr E_BIN;
run;
```

where pe_comb includes the estimates results, and var_comb includes the variance information.

If the datasets between imputations are identical after multiple imputation step, which will cause the SAS procedure proc mianalyze not runnable, the dataset with _imputation_=1 will be used to create the results.

95% confidence limits by Wilson score method with continuity correction:

For primary analysis, 95% confidence limits will be calculated by Wilson score method with continuity correction using the following formula:

$$\frac{\left(2\bar{Q}_m + \frac{1}{n} + \frac{t^2}{n} + \frac{t^2 r_m}{n}\right)}{2\left(1 + \frac{t^2}{n} + \frac{t^2 r_m}{n}\right)} \pm \sqrt{\frac{\left(2\bar{Q}_m + \frac{1}{n} + \frac{t^2}{n} + \frac{t^2 r_m}{n}\right)^2}{4\left(1 + \frac{t^2}{n} + \frac{t^2 r_m}{n}\right)^2} - \frac{\left(\bar{Q}_m^2 + \frac{1}{4n^2} + \frac{\bar{Q}_m}{n}\right)}{\left(1 + \frac{t^2}{n} + \frac{t^2 r_m}{n}\right)}}$$

where

\bar{Q}_m is “Estimate” in pe_comb;

$r_m = \left(1 + \frac{1}{m}\right) B_m / \bar{U}_m$;

B_m and \bar{U}_m are “BetVar” and “WinVar” in var_comb, respectively;

n is the subgroup sample size;

t is the 95% quantile of t_v -distribution, with $v = (m - 1)(1 + 1/r_m)^2$ degrees of freedom;

m is the number of imputed datasets.

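### The pooled 95% interval for the primary endpoint is built with the 95% t quantile and the wrong continuity-correction sign for the lower limit, so as written it is about a 90% interval shifted slightly upward.

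*SAP*

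**What the plan says.** Protocol 12.4.2 sets the method for the primary endpoint: "The corresponding 95% confidence interval also will be derived based on the score method including continuity correction". SAP 2.5.2 repeats it: "The corresponding 95% confidence interval for response rate also will be derived based on the score method including continuity correction".

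SAP 5.5.1, added with the sample code in Amendment 3, turns this into steps. Step 2 runs `proc freq` on each imputed dataset with the `wilson(correct)` option, which "is used to calculate the 95% confidence intervals by Wilson score method with continuity correction". Step 3 combines the imputations by Rubin's rules. The section then says that "95% confidence limits will be calculated by Wilson score method with continuity correction using the following formula" and prints one expression with a plus-or-minus sign before the square root. In that expression the centre contains +1/n, and the constant under the root is Q² + 1/(4n²) + Q/n. Both serve the lower and the upper limit alike. The critical value t "is the 95% quantile of" the t distribution with v = (m − 1)(1 + 1/r_m)² degrees of freedom.

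If all imputed datasets are identical, `proc mianalyze` cannot run, and "the dataset with _imputation_=1 will be used to create the results".

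**The concern.** There are two separate departures from a 95% continuity-corrected Wilson interval.

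- **Quantile.** The expression returns both roots of a quadratic, so t cuts off both tails. With the 95% quantile, 5% is left in each tail and the nominal level is 90%.
- **Sign.** A continuity-corrected score interval moves the lower limit down and the upper limit up. The printed constant equals (Q + 1/(2n))², so both limits are computed as if the observed rate were Q + 1/(2n). That is right for the upper limit. For the lower limit it raises the bound instead of lowering it, so the correction adds no width.

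SAP 2.5.2 plans no inferential methods, so the response rate and its interval are the whole primary result, both for the retreated subjects and for those who had responded in the core studies. The sample size section is also argued from interval width. An interval reported as 95% with about twice the stated error rate would overstate the precision of that result.

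**Working it through.** **Inputs**

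- Response rate Q = 0.55 (SAP 3.1).
- n = 225, 405 and 540: the 250, 450 and 600 per group of SAP Table 3-1, less 10% drop-out.
- r_m, the ratio of between-imputation to within-imputation variance including the factor (1 + 1/m), and m, the number of imputations, are not given. r_m = 0 is used as the limiting case, and r_m up to 0.6 as an assumed range.
- Quantiles for large v: 95% gives 1.645; 97.5% gives 1.960.

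**The plan's own planning figures.** Table 3-1 gives 48.6% to 61.6% for 250 per group. A simple two-sided normal (Wald) interval on 124/225 with 1.96 gives 48.61% to 61.61%. The other rows also reproduce: 223/405 gives 50.22% to 59.91%, and 297/540 gives 50.80% to 59.20%. Planning therefore used the 97.5% quantile.

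**What the printed formula solves.** Write k = t²(1 + r_m)/n. Both printed limits are the roots in p of (Q + c − p)² = k·p(1 − p) with c = +1/(2n). The standard interval takes the smaller root with c = −1/(2n) and the larger root with c = +1/(2n).

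**Worked case, n = 225, r_m = 0**

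*As printed, t = 1.645:*
- k = 1.645²/225 = 0.01202
- centre = (1.1 + 0.00444 + 0.01202)/(2 × 1.01202) = 0.5516
- half-width = √(0.5516017² − 0.3049494/1.0120246) = 0.0542
- limits **49.74% to 60.58%**, width 10.8 points

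*Correct, t = 1.960:*
- k = 1.960²/225 = 0.01707
- lower centre = (1.1 − 0.00444 + 0.01707)/(2 × 1.01707) = 0.5470, half-width 0.0645, lower limit 48.25%
- upper centre = (1.1 + 0.00444 + 0.01707)/(2 × 1.01707) = 0.5513, half-width 0.0644, upper limit 61.58%
- limits **48.25% to 61.58%**, width 13.3 points

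**Other sizes (r_m = 0, rate 55% unless stated)**

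| n | As printed | Correct |
|---|---|---|
| 405 | 51.04–59.14% | 50.01–59.90% |
| 540 | 51.56–58.58% | 50.69–59.24% |
| 80, rate 70% (assumed, for a smaller responder subgroup) | 61.7–78.2% | 58.6–79.5% |

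With r_m = 0.10, m = 100 and n = 225, the limits are 49.47–60.84% as printed and 47.93–61.88% when correct. The gap is not special to r_m = 0.

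**Separating the two errors and their coverage.** Limits are for n = 225, Q = 0.55, r_m = 0. Coverage is exact binomial, averaged over true rates 0.40 to 0.90.

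| Version | Limits | Coverage | Lower limit above truth | Upper limit below truth |
|---|---|---|---|---|
| As printed | 49.74–60.58% | 89.9% | 5.7% | 4.4% |
| Quantile error only | 49.30–60.58% | 91.5% | 4.1% | 4.4% |
| Sign error only | 48.69–61.58% | 95.0% | 2.8% | 2.2% |
| Correct | 48.25–61.58% | 95.8% | 2.0% | 2.2% |

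For the printed formula, average coverage is 89.5% at n = 50, 89.8% at n = 100, 89.9% at n = 405 and 90.0% at n = 540.

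**Consistency within SAP 5.5.1.** As r_m tends to 0, the pooled formula should reduce to the Step 2 limits. It does not. If the identical-imputation fallback reports those Step 2 limits, which the text implies but does not state, an arm with no imputation variance gets the 13.3-point interval. At n = 225 and large v, an arm with imputed data gets 11.4 points at r_m = 0.1, 13.2 at r_m = 0.5 and 13.7 at r_m = 0.6. Up to r_m of about 0.5, missing data would appear to improve precision.

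**The case against.** The strongest reply is that the wording about the quantile is loose. The surrounding text says 95% throughout, Step 2 asks for standard 95% limits, and Table 3-1 was computed with 1.96, so a programmer might use the two-sided critical value anyway. The 90% coverage follows only if t is coded as defined. That is fair, but this sentence is the operative definition of t in the final-analysis code, and reading it correctly requires overriding it.

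Second, the sign error alone does little harm. With the 97.5% quantile, coverage is still 95.0% and only the lower limit moves, by 0.44 points at n = 225. This stands: the sign is a departure from the named method, not a material loss of coverage. It matters more in small groups (about 1.3 points at n = 80, rate 70%).

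Third, the excess error is not purely optimistic. At n = 225 the lower side gains about 3.7 points of error (5.7% against 2.0%) and the upper side about 2.2 (4.4% against 2.2%). Both tails are too large, the lower one more so.

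Fourth, r_m = 0 is a limiting case, because identical imputations go to the fallback and v is undefined there. The results at positive r_m show the same gap. The claim that imputed data give a narrower interval does depend on r_m and fails above about 0.5 in the case worked here.

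Last, the analysis is descriptive, the programme has been discontinued, and no decision rule uses the limits. The point estimate is unaffected. This limits the consequence to a wrong confidence level and overstated precision, but it does not make the reported interval correct.

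**Conclusion.** The concern holds. Implemented as written, SAP 5.5.1 produces about a 90% interval under a 95% label for the primary endpoint, contradicting Protocol 12.4.2, SAP 2.5.2 and its own Step 2. At n = 225 and a 55% rate, the interval is 10.8 points wide instead of 13.3, about 19% too narrow (2.5/13.3), and its lower limit is 1.5 points too high (49.74 against 48.25). The quantile is the main error and the sign is secondary. The size rests on t being programmed as defined, the planning rate and sample sizes, and large v. The conclusion does not change for r_m from 0 to 0.2 with m from 20 to 100. The formula was read from an extracted PDF, but its plus signs agree in every place where the correction enters, so a reading error is unlikely. It should be corrected before the limits are reported.

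**What to change.** In SAP 5.5.1:

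1. Define t as the 97.5% quantile of the t distribution with v degrees of freedom.
2. Give the limits separately. For the upper limit, keep +1/n in the centre (also where it is squared) and +Q/n in the constant, and take the plus root. For the lower limit, use −1/n and −Q/n in the same places, and take the minus root.
3. State that the identical-imputation fallback reports the Step 2 `wilson(correct)` limits.
4. Add a program check that setting r_m = 0 and t = 1.960 reproduces `wilson(correct)` from `proc freq`. For n = 225 and a rate of 0.55, the formula should return 48.25% to 61.58%.

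The cost is a few lines of SAP text and code. No data collection or point estimate changes. The reported interval becomes wider by about 23% in the worked case (13.3 against 10.8 points), which is the precision the plan meant to report.
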